For the survival analysis, we will create two sets of variables indicating retention using a 28 day cutoff and using a 90 day cutoff to reflect the fact that the national guidelines for retention in HIV services changed from 12 weeks (i.e. 90 days) to 4 weeks (i.e. 28 days). For each recorded visit, we will also assess whether the participant is within their scheduled window and the number of days between the scheduled visit date and the date the visit was actually attended (v1 denotes the first attended visit after study enrollment; v2, v3, v4, etc. will be calculated for all visits between study enrollment and date of EL questionnaire (or date EL questionnaire should have been conducted, based on enrollment date, for those LTFU in the study at endline):

For each visit, starting at visit 2 (i.e. v2):

- v2_days_aftersched = [visit date (v2q036)] [date of prior scheduled visit (v1q044)]; missing if either date is . or jan 1 1990
- v2_ltfu_28 = 1 if v1_days_aftersched >28; = 0 if v1_days_aftersched ≤28; missing if next scheduled visit date (v1q044) is missing (. or jan 1 1990).
- v2_ltfu_90 = 1 if v1_days_aftersched >90; = 0 if v1_days_aftersched ≤90; missing if next scheduled visit date is missing (. Or jan 1 1990).

1tfu 28 LTFU status for survival analysis using 28 day cutoff

- **ltfu_28**=1; lost to follow-up
 - o v2 ltfu 28==1 OR v3 ltfu 28==1 OR v4 ltfu 28==1, etc.
 - o Appears retained for all recorded visits, but earliest value of today_el, today_el_approx, latest_mre falls MORE than 28 days after latest instance of vnq044
- ltfu 28=0; retained

- o v2 ltfu 28==0 AND v3 ltfu 28==0 AND v4 ltfu 28==0, etc. AND the earliest value of today el, today el approx, latest mre falls within 28 days of latest instance of **vnq044**
- 1tfu 28=8; transferred out
 - o Retained up to the date of transfer (transfer==1 and q027, transfer date, must be non-missing)
- **ltfu 28**=9; died
 - o Retained up to the date of death (death==1 and q028, death date, must be non-missing)

1tfu 90 LTFU status for survival analysis using 90 day cutoff

- **ltfu 90**=1; lost to follow-up
 - o v2 ltfu 90==1 OR v3 ltfu 90==1 OR v4 ltfu 90==1, etc.
 - o Appears retained for all recorded visits, but earliest value of today el, today el approx, latest mre falls MORE than 90 days after latest instance of **vnq044**

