Code: egen n_missed_28=rowtotal(v2ltfu_28 v3ltfu_28 v4ltfu_28 v5ltfu_28 v6ltfu_28 v7ltfu_28 v8ltfu_28 v9ltfu_28 v10ltfu_28 v11ltfu_28)

mean_followup_mo=Mean months of follow-up time during the study period

• Code: forvalues i=1/11{

```
gen v`i'fu=v`i'followup if ((v`i'q036<=today_el & today_el!=.) |
(v`i'q036<=today_el_approx & today_el_approx!=.))
}
egen followup_total=rowtotal(v1fu v2fu v3fu v4fu v5fu v6fu v7fu v8fu v9fu
v10fu v11fu)
gen mean_followup=followup_total/n_visits
gen mean_followup_mo=floor(mean_followup/30.44)
replace mean_followup_mo=1 if mean_followup_mo==0</pre>
```

Timeliness of scheduled intervention activities

Timeliness of each scheduled intervention activity, including scheduled postings and group chats, will be calculated using Facebook group data from Grytics to evaluate the extent to which each group was implemented as planned. The difference between the scheduled date and the actual date will be calculated for each intervention activity; timeliness will be dichotomized with activities coded as timely if they occurred within one week of the scheduled time, and untimely if they occurred outside of this one-week window. The proportion of missing data will be reported.

High and low intervention engagement

Facilitators will be asked to identify the highest- and lowest-engaged participants in their Facebook groups. High and low engagement participants will be recruited at endline to participate in IDIs.

Social Support [MOS-SSS]¹

People sometimes look to others for companionship, assistance, or other types of support. How often is each of the following kinds of support available to you if you need it?

Factor	Item	Item
	no.	
Emotional/	1	Someone you can count on to listen to you when you need to talk
support	2	Someone to give you information to help you understand a situation
	3	Someone to give you good advice about a crisis
	4	Someone to confide in or talk to about yourself or your problems
	5	Someone whose advice you really want

	6	Someone to share your most private worries and fears with
	7	Someone to turn to for suggestions about how to deal with a personal problem
	8	Someone who understands your problems
Tangible support	9	Someone to help you if you were confined to bed
	10	Someone to take you to the doctor if you needed it
	11	Someone to prepare you meals if you were unable to do it yourself
	12	Someone to help with daily chores if you were sick
Affectionate support	13	Someone who shows you love and affection

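### The visit-level loss flags behind the primary endpoint (28-day and 90-day) are set from `v1_days_aftersched`, which the SAP never defines; coded literally, the pattern shifts failures by one visit

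*SAP*

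**What the plan says.** All of the following is in SAP section IV.C, Retention for survival analysis, unless another place is named.

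- **Visit numbering:** "v1 denotes the first attended visit after study enrollment". The visit-level variables are then built in turn: "For each visit, starting at visit 2 (i.e. v2").
- **Lateness:** "v2_days_aftersched = [visit date (v2q036)] [date of prior scheduled visit (v1q044"). The minus sign between the two dates seems to have been lost in the text extraction. The quantity is the date visit 2 was attended minus the date set for it at visit 1, and it is missing if either date is missing.
- **28-day flag:** "v2_ltfu_28 = 1 if v1_days_aftersched >28". The flag is 0 at 28 days or fewer, and missing if the scheduled date `v1q044` is missing.
- **90-day flag:** "v2_ltfu_90 = 1 if v1_days_aftersched >90; = 0 if v1_days_aftersched ≤90".
- **Participant status:** `ltfu_28` equals 1 if any visit flag from v2 on equals 1. A second, separate route also gives loss: all recorded visits look on time, but the earliest of the endline date, its approximation and the last record extraction falls more than 28 days after the latest scheduled date (`vnq044`).
- **Failure time:** for a lost participant, `ret_time_28` runs from baseline to the latest scheduled date before the loss.
- **Use:** section VI, Objective 1, takes `ltfu_28` as the failure variable and `ret_time_28` as the time variable of the log-rank analysis, with exit at day 270. The same flags are summed for the missed-visit count: "egen n_missed_28=rowtotal(v2ltfu_28 v3ltfu_28" and so on to v11.

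**The concern.** The flag for visit 2 points to a variable that is not created. Lateness begins at visit 2 because the scheme gives visit 1 no earlier scheduled date to be compared with. The line cannot be run as it stands, so the analyst has to guess a repair to the primary-outcome rule.

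One possible guess does harm. If the written pattern (flag N from lateness N-1) is carried forward, the code runs without complaint from visit 3, because `v2_days_aftersched` and later variables do exist. Each flag would then describe the visit before it. Failures would be dated one appointment late, and a late last visit could have no flag to carry it. This would reach the primary log-rank test, its 90-day secondary version and the missed-visit counts.

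**Working it through.** The plan gives no figure on this point to reproduce. The check sets the definitions side by side, applies them to constructed visit histories, and then illustrates the size by simulation.

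**1. Indices side by side**

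| Item | Index used |
|---|---|
| Lateness at visit 2 | `v2q036` minus `v1q044`, named `v2_days_aftersched` |
| Missing rule of the visit 2 flag | `v1q044`, a component of `v2_days_aftersched` |
| Comparison in the 28-day and 90-day flags | `v1_days_aftersched`, not defined |

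Two of the three items agree with each other. The comparison does not, in either flag.

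**2. Constructed histories**

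Appointments are 30 days apart and endline is day 270. When the flag of visit N fires, the failure date is taken as the date scheduled at visit N-1. Three codings are compared: the flag from the same visit's lateness; the shifted flag on recorded visits only; and the shifted flag on every slot up to v11.

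| History | Same visit | Shifted, recorded visits | Shifted, all slots |
|---|---|---|---|
| v2 due day 60, attended day 100, then on time | lost, day 60 | lost, day 130 | lost, day 130 |
| v3 due day 90, attended day 130, then on time | lost, day 90 | lost, day 160 | lost, day 160 |
| Final visit due day 210, attended day 250, next date day 280 | lost, day 210 | retained | lost, day 280 |
| Final visit due day 150, attended day 190, next date day 220, no more visits | lost, day 150 | lost, day 220 (latest-scheduled-date rule) | lost, day 220 |

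In the third row the all-slots coding keeps the failure but dates it at day 280. That is after the exit at day 270, so the log-rank test treats the participant as censored.

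**3. Illustrative size**

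Assumptions, none of them from the documents: first visit between day 1 and day 30; 30-day intervals; at each visit a probability q of being 29 to 60 days late, otherwise 0 to 7 days late. The latest-scheduled-date rule and the 270-day exit are applied. With q = 5%, the share of participants with a primary event is:

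- same-visit flag: 27.7%
- shifted, recorded visits: 23.7%, so the share of events lost is (27.7 - 23.7)/27.7 = 14.4%
- shifted, all slots: 24.2%, so the share lost is (27.7 - 24.2)/27.7 = 12.6%

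A separate run of the same setting gave 23.5% for recorded visits, a loss of (27.7 - 23.5)/27.7 = 15.2%. The range is therefore about 13 to 15%.

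For the recorded-visits coding, other values of q give similar relative losses: q = 2%, (12.1 - 10.3)/12.1 = 14.9%; q = 10%, (49.1 - 42.5)/49.1 = 13.4%.

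**4. Late final visits that are still counted**

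Under the recorded-visits coding, 10%, 19% and 35% of participants with a late final visit were still classed as lost (q = 2%, 5% and 10%), through the latest-scheduled-date rule or an earlier late visit.

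**The case against.** The strongest reply is that this is a slip of one digit and that nothing else in the SAP supports a shifted rule.

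- The flag's missing rule names `v1q044`, which belongs to visit 2's lateness. The lead-in describes the quantity as the gap between the scheduled and attended dates of each recorded visit. The missed-visit count is described in terms of the visit itself.
- The SAP is loose with example indices elsewhere. The endline status definition pairs `v5q036` with `v3q044`. The code for the missed-visit count writes `v2ltfu_28` where the definition writes `v2_ltfu_28`, so the definition is not evidently the executed code.
- Only the visit 2 lines are written out. How visits 3 to 11 are coded is not shown.

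All of this stands, and it makes the slip the likeliest explanation. It does not remove the need for a correction, because the text serves as the programming specification for the primary endpoint and the line as written cannot be run.

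A reader might infer two stronger things that the documents do not support. One is that every flag is in fact shifted; that extends a pattern from the single visit written down. The other is that a late final visit is never counted as a failure. That is untrue even under literal coding, because the latest-scheduled-date rule, an earlier late visit, or a flag in the next slot can still produce a loss. The next-slot reading is not harmless either: it leaves the number classed as lost unchanged but pushes some failures past day 270.

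**Conclusion.** The inconsistency is real and sits in both visit-level flags that feed `ltfu_28` and `ltfu_90`. It is most likely a subscript error for `v2_days_aftersched`. If the program uses the same visit's lateness, no events are lost. If it carries the written pattern to later visits, failure times move one appointment later and, with an assumed 5% chance of lateness per monthly visit, about 13 to 15% of primary events drop out of the 270-day analysis. The size depends on the assumed lateness and visit interval and is not an estimate for this trial.

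A reader might also infer a biased treatment effect. The documents do not support that: the same rule applies in both arms, and the direction of any effect on the comparison cannot be stated. The point should be corrected because it defines the primary outcome.

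**What to change.** In SAP section IV.C:

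1. Define `vN_ltfu_28` and `vN_ltfu_90` from `vN_days_aftersched` of the same visit, for every N from 2 on.
2. Set the flag to missing, not to 1, when either the visit date or the prior scheduled date is missing. The present flag rule names only the scheduled date, so it does not say what happens when a visit date is absent.
3. State that an unattended last appointment is handled only by the rule based on the latest `vnq044`.
4. Check that the program for `ltfu_28`, `ltfu_90`, `ret_time_28`, `ret_time_90` and `n_missed_28` follows this, and record the check.

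The cost is an index and missing-rule correction in the text and a check of the program. If the program proves to be shifted, the affected variables and analyses must be re-run. No new data are needed.

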 - q027>today_bl AND latest follow-up date prior to transfer is missing
 t ltfu 90=9
- if **ltfu_90=9**
 - o ret_time_90=q028-today_b1

Missingness will be handled in the following way:

- If a follow-up date (i.e. **v7q044**) is missing (. or Jan 1 1990) and retained up to that point, retention must be assessed using the clinic visit date at which the follow-up date is missing. Consider retention time to be the visit date + 28 days as a conservative estimate of the follow-up time. Consider censored if retained up to that point.
- If a participant has died [died==1] but is missing date of death [q028] and appears to be retained throughout the entire study period, retention time is assessed based on the latest attended visit (i.e. v2q036), given that we do not know if participant died prior to the scheduled follow-up date.
- If a participant has transferred [transfer==1] but is missing date of transfer [q027] and appears to be retained throughout the entire study period, participant is categorized as transferred (ltfu_28/ltfu_60/ltfu_90==8) and retention time is assessed based on the latest available follow-up date (i.e. v7q044)
- If medical record data are incomplete towards the end of the study period (i.e. **latest_mre** falls before **today_el/today_el_approx**), then retention is assessed using **latest_mre** as the pseudo-endline date. Retention cannot be assessed into the future.
- If no visit data for participant during the study period or all visit dates for participant are missing during the study period (. or jan 1 1990), then retention time is missing and LTFU status is missing.
- We will generate a variable, conservative, to indicate whether participants have complete medical record data (conservative=1) or have a gap during the beginning of the study period conservative=.).

conservative=1 if (v1q036-today_bl)<=56 & v1q036!=.

conservative=. otherwise

Other variables for descriptive analysis of retention data

Other variables will be created to describe retention and clinic visits during the study period:

n_visits=number of clinic visits attended during the study period

• Code:gen n_visits=.

```
forvalues i=11(-1)1 {
replace n_visits=`i' if v`i'q036!=. & n_visits==. & ((v`i'q036<=today_el &
today_el!=.) | (v`i'q036<today_el_approx & today_el_approx!=.))
}
replace n visits=0 if v1q036==. | ( v1q036<today bl & v2q036==.)</pre>
```

n missed 28=Number of clinic visits missed by more than 28 days during the study period

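### The SAP's rules for a blank next-appointment date in mid-course conflict: a participant who keeps attending gets either no primary-outcome status or early censoring

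*SAP*

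**What the plan says.** All the rules are in SAP section IV.C, Retention for survival analysis. They produce `ltfu_28` and `ret_time_28`, the failure and time variables of the primary log-rank analysis (section VI, Objective 1), which stops at 270 days.

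- **Visit flag.** Each attended visit is compared with the date scheduled at the visit before. The flag is "missing if next scheduled visit date (v1q044) is missing (. or jan 1 1990".
- **Retained.** "v2 ltfu 28==0 AND v3 ltfu 28==0 AND v4 ltfu 28==0, etc. AND the earliest value" of three closing dates must lie within 28 days of the last scheduled date.
- **Lost.** Either "v2 ltfu 28==1 OR v3 ltfu 28==1 OR v4 ltfu 28==1, etc", or a second branch: "Appears retained for all recorded visits, but earliest value of today_el, today_el_approx, latest_mre falls MORE than 28 days after" the last scheduled date.
- **Missing follow-up date, participant retained so far.** "retention must be assessed using the clinic visit date at which the follow-up date is missing". Then: "Consider retention time to be the visit date + 28 days as a conservative estimate of the follow-up time". And: "Consider censored if retained up to that point".
- **Time.** `ret_time_28` is defined for four statuses only: retained, lost, transferred, died. Its missing-date branch for the retained concerns the latest follow-up date, not one in the middle of the record.
- **Missing outcomes.** Primary analyses are complete case (section IV, Missing data), and the multiple imputation under Objective 1 is triggered only by variables other than retention.

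No sentence covers a blank date followed by further recorded visits. The 90-day variables copy the structure.

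**The concern.** The SAP expects blanks: it names a placeholder date for them and writes several missing-date branches. A participant who attends many visits has many chances of one blank, so the people most exposed are those who stayed in care. If such a person cannot be coded as retained, complete-case analysis removes a success. If the person is censored soon after the blank, documented attendance and any later loss go unused. The two rules also give different answers for the same record. In an open-label trial, the choice between them on the primary endpoint should not be left to whoever writes the code.

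**Working it through.** **The plan's own figure.** Inputs (SAP section III): 12-month retention 0.45 and 0.575, 80% power, two-sided 5%, 10% loss, exponential times. HR = ln 0.575 / ln 0.45 = 0.693. Schoenfeld events = 4(1.960 + 0.842)² / (ln 0.693)² = 234. With loss as exponential censoring, the mean event probability is 0.4655, so N = 234 / 0.4655 = 503, against the stated 500. These hazards are used below.

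**Example histories.** Visits every 30 days from day 30 (the protocol describes monthly attendance), blank next-appointment date at visit 3 (day 90), cut-off day 270. I take each visit's flag from that visit's own lateness; the printed formula carries the index of the visit before.

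| History | Status rules, read literally | Missing-date rule, read literally |
|---|---|---|
| (a) attends all nine visits; flags 0, 0, missing, 0, 0, 0, 0, 0 | neither retained nor lost | censored day 90 + 28 = 118 |
| (b) visit 7 attended 35 days late | lost, through the any-flag rule | censored day 118 |
| (c) stops after visit 6 (day 180) | lost only if a missing flag counts as appearing retained; otherwise no status | censored day 118 |

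Without the blank, (a) is retained to day 270, so censoring discards 270 − 118 = 152 days of documented attendance. Comparing (a) with (b), the status rules drop the stayer and keep the later loss, which is selection on the outcome. In all three, the interval from visit 3 to visit 4 is not tested: lateness cannot be computed, or follow-up has already ended.

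**Share affected (assumed blank rate q per visit).** A full attender has eight visits followed by another, so the share with an interior blank is 1 − (1 − q)⁸: 7.7% at 1%, 21.6% at 3%, 33.7% at 5%.

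**Simulation.** 250 per arm, monthly visits, 270 days, same q in both arms, no site strata or extra dropout, 1,500 runs per rate. A loss counts if the missed appointment falls by day 240, so that the 28-day grace ends before day 270. Retention is control / intervention.

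| q | Handling | n | Events | Retention | Power |
|---|---|---|---|---|---|
| 1% | full data | 500 | 179 | 0.591 / 0.695 | 0.679 |
| | censor at blank + 28 | 500 | 174 | 0.588 / 0.692 | 0.667 |
| | status rule, later losses kept | 475 | 179 | 0.571 / 0.677 | 0.677 |
| | status rule, all blank cases out | 471 | 174 | 0.577 / 0.682 | 0.665 |
| 5% | full data | 500 | 178 | 0.592 / 0.695 | 0.673 |
| | censor at blank + 28 | 500 | 159 | 0.579 / 0.684 | 0.621 |
| | status rule, later losses kept | 392 | 178 | 0.491 / 0.602 | 0.612 |
| | status rule, all blank cases out | 373 | 159 | 0.519 / 0.630 | 0.589 |

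The two status-rule rows correspond to letting, or not letting, a missing flag pass as appearing retained in the second lost branch. Full-data power varies by simulation error between settings, so compare within a rate.

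- **Censoring.** Events lost: 5/179 = 3% at 1% and 19/178 = 11% at 5%. Power falls by 1 and 5 points.
- **Status rule.** Control retention falls by 1.4 to 2.0 points at 1% and 7.3 to 10.1 at 5%; intervention by 1.3 to 1.8 and 6.5 to 9.3.
- **Between arms.** The difference is 0.104 with full data at 5%, 0.105 with censoring and 0.111 under either status-rule row.

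**Second set-up.** 600 trials per rate, with the hazard running over the full 270 days. Full-data control retention is then 0.45^(270/365) = 0.554, against 0.45^(240/365) = 0.591 above. Events lost to censoring were 3% at 1% and 13% at 5%, and power at 5% fell from about 73% to 67%. Dropping all blank cases lowered retention from 55.4% to 54.0% at 1% and 48.5% at 5% (control), and from about 66.5% to 65.2% and 60.2% (intervention), with power about 61% at 5%.

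**The case against.** A sensible reading exists. The time variable ties visit + 28 days to a missing latest date. The second lost branch speaks of recorded visits. The SAP's code for counting missed visits sums across flags and treats missing ones as zero. Since the flags run to visit 11, and anyone with fewer visits has missing later flags, a missing flag can hardly have been meant to disqualify. On this reading a blank is simply untested and later visits count. That stands as the probable intent, and it rules out the claim that no reading keeps the later visits. But the missing-date rule carries no such limit, the retained rule is written as equality to 0, and even this reading never tests the interval after the blank.

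A reader might infer that every later loss leaves the analysis. It does not: the any-flag rule still counts a later visit more than 28 days late. Later losses leave only if the missing-date rule governs or, for people who never return, if a missing flag bars appearing retained.

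A reader might also take the large falls in retention as the expected harm. They arise only if the missing-date rule, which does supply a status and a time, is set aside and the status rule is read strictly.

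Finally, the SAP plans regular completeness checks, which may keep blanks rare.

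**Conclusion.** The point holds as a conflict between two rules that define the primary endpoint, neither of which handles an interior blank properly. Its size depends on a blank rate that the documents do not give. At 1% it is small under censoring: about 3% of events and about 1 point of power. At 5%, censoring costs 11% to 13% of events and about 5 to 6 points of power, and the strict status rule lowers retention by 6 to 10 points.

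Both arms shift alike, so no between-arm bias is shown; because the simulations used equal blank rates, they say nothing about unequal ones. The harm shown is to absolute retention and to power. With an unknown rate and a plausible benign intent, this is a should-fix; the documents do not support calling it a must-fix.

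**What to change.** 1. Limit the rule that censors at visit + 28 days to the last recorded visit, as the time definitions already imply.
2. Define `ltfu_28` = 0 as no recorded-visit flag equal to 1, plus the existing terminal check, and keep all visits and flags after a blank.
3. For the interval after an interior blank, pre-specify a substitute due date from the participant's own previous recorded appointment interval. State a fallback for a blank at the first visit, where no earlier interval exists. Use visit + 28 days only as a sensitivity analysis: with the 28-day cutoff it codes any return after day 56 as lost, so someone given a two-month appointment who attends on time at day 60 would become an event. The SAP uses that value as a conservative follow-up time, not as a due date for declaring loss.
4. Report the number of interior blanks by arm.
5. Apply the same changes to `ltfu_90` and `ret_time_90`.

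The cost is SAP wording and a few lines of code, with no new data. The downside is that the substitute due date is approximate.
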